## Definitions and nomenclature

Spinal cord stimulation (SCS) will be performed using a 32-electrode paddle array (Boston Scientific, Marlborough, MA) (Figure 1) implanted in the dorsal epidural space along the thoracolumbar region of the spinal cord. The array will be powered by a multiple independent current-controlled (MICC) implantable pulse generator (IPG) connected to the paddle per standard of care procedures for SCS implantation. In addition, as per standard of care, motor evoked potential (MEP), somatosensory evoked potential (SSEP) and electromyography (EMG) will be performed via the IOMAX intraoperative neuromonitoring system (Cadwell, Kennewick, WA) and LR10 (Tucker Davis Technologies, Alachua, FL) recording device. **The SCS system will be placed for clinical purposes, i.e., treatment of chronic pain, however, we will collect data at various points during the placement. The study procedures will add 15 minutes to the surgery.** MUSC's Locomotion Rehabilitation Laboratory – located at the College of Health Professions Building C - houses a Biodex Pro System 4 isokinetic/isometric dynamometer (Biodex Medical Systems, Shirley, NY). The Biodex will standardize application of passive isokinetic knee flexion/extension trials to each blinded subject for proprioceptive investigations, which will be referred to as threshold to detect passive movement (TTDPM) throughout the rest of this document. Finally, MUSC's Locomotor Energetics and Assessment Laboratory – also located at the College of Health Professions Building C – houses a dual belt Instrumental Treadmill (Bertec, Scotland, U.K.) that is coplanar with the floor and will be used during all walking events. The laboratory also has a 12-camera motion capture system (PhaseSpace, San Leandro, CA) that utilizes active infrared LED tracers to track kinematic positioning data and will be used during all walking events. Another tool offered by the lab is a 16-channel EMG system (Motion Labs, Baton Rouge, LA, model MA300-XVI) which utilizes surface electrodes to detect target muscle activity and will also be used during all walking events. In all, we expect total duration of the study to be approximately 30 days.

[figure not shown]

Figure 1: Boston Scientific CoverEdge™ 32 Surgical Lead (left) and fluoroscopic image of the stimulator array after implantation along the dorsal epidural space (right).

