## **9.0 Study Design / Methods**

### **Step 1: Recording and stimulation of spinal potentials during insertion of epidural spinal stimulator paddle**

On the day of the surgery, subjects will first be placed under general anesthesia for the procedure. Next, after positioning the subject on the operating room table, subdermal MEP, SSEP and EMG needle electrodes will be placed throughout the body by the neurophysiology team as determined by standard of care guidelines. Once the epidural paddle is placed by the surgeon, study procedures will begin by (#1) connecting the terminals of the paddle to the LR10 (Tucker Davis Technologies, Alachua, FL) for amplification, filtering and recording of electrophysiological signals. Using this recording setup, (#2) MEP and SSEP protocols will be performed to determine motor and sensory thresholds, respectively. Next, the surgical procedure will resume and after the IPG has been placed, study procedures will begin again and include (#3) activation of both low-frequency tonic stimulation (LFTS) and high-frequency burst stimulation (HFBS) patterns from the inserted paddle while recording EMG signals. The surgical procedure being performed (SCS paddle and IPG implantation) for

Date: 8/1/19

Version: 01

clinical purposes will not deviate in any way from standard of care. The recording and stimulation study procedures will occur using equipment already present in the operating room used to test the SCS system as per standard of care in addition to the LR10 (Tucker Davis Technologies, Alachua, FL) signal recording machine. All devices will be used for their FDA-approved intended use. Our study procedures are expected to add approximately 15 minutes to the SCS procedure and will be paid for by internal funds. The standard of care versus the research procedures are diagramed below:

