### **Step 2: Proprioception testing before, during and after SCS stimulation**

All of the following are for research purposes and not considered standard of care for SCS surgery. Following an approximately 30-day recovery period from surgical placement of the paddle and IPG, subjects will undergo

Date: 8/1/19

Version: 01

stimulation configuration mapping (SCM) in the Locomotor Rehabilitation Laboratory at the College of Health Professions Building C at MUSC in order to determine electrode and parameter configurations that elicit activation of lower extremity musculature. For this testing, we will place surface EMG pads on subjects' skin overlying muscles of interest. Using the Boston Scientific external stimulator interface, we will wirelessly activate the implanted spinal paddle and compare muscle activation using LFTS and HFBS patterns by systematically testing each individual contact. Subjects will comfortably lie supine on a large, low-rise rehabilitation mat common to any physical rehabilitation clinic during SCM.

Next, we will investigate the perceived change in knee joint angle and direction of movement reported by the subject in a Threshold to Detect Passive Movement (TTDPM) task. The TTDPM protocol will begin with the subject sitting in the Biodex testing seat, with the non-tested leg hanging freely and the tested leg strapped to the rotating arm of the dynamometer at the lower shank. The subject will be blinded as to the mode and intensity of stimulation: HFBS, LFTS, or no stimulation. Furthermore, in order to shield the subject from witnessing initiation, direction and approximate distance traveled of the shank, the subject will be asked to wear a blindfold and headphones playing a soft background noise (Figure 3). The TTDPM will consist of at least 10 trials for each stimulation condition. The subject has control of a switch that immediately halts movement of the rotating arm, which is to be activated once the subject perceives movement **OR** if the subject begins to feel any pain or discomfort throughout the task. Our research team anticipates data collection to last approximately 3 hours per subject for this step (1 hour for supine SCM, 1 hour for TTDPM and 1 hour for set up and breakdown). Proprioception testing will take place before, during and after SCS stimulation.

Figure 3: TTDPM test using a Biodex

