Through EMG capture and high/low bandpass filtering to extinguish biologic artifact and equipment artifact respectively, segments of EMG that were recorded through functional task can be analyzed with an algorithm that yields hierarchical complexities representative of muscle synergies. The research team will use previously outlined methodology to define modules through non-negative matrix factorization, where analysis will be applied to consecutive gait cycles.

The Instrumental Treadmill (Bertec, Scotland, U.K), GAITRite mat (CIR Systems, Franklin, NJ), motion capture system (PhaseSpace, San Leandro, CA), and MA300 EMG system (Motion Labs, Baton Rouge, LA) have been used in the same manner described above in the following MUSC IRB approved protocols: **Pro00028941**, Assessment of contributions to impaired walking after neurologic injury; **Pro00088728**, Fatigue and mobility in stroke: a biomechanical and neurophysiological investigation; **Pro00048394**, The effects of impaired post-stroke coordination and motor pathway integrity on mobility performance; **Pro00059390**, A novel mechanics-based intervention to improve post-stroke gait stability.

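### No masking is described for those who read the Aim 1 EMG responses or process the Aim 3 gait EMG, and the rules that would limit their judgement are not stated

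*Combined protocol and SAP*

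**What the plan says.** **Masking.** Section 9.0, Step 2 states, for the TTDPM task: "The subject will be blinded as to the mode and intensity of stimulation: HFBS, LFTS, or no stimulation". Section 3.0, Definitions and nomenclature, agrees, describing "passive isokinetic knee flexion/extension trials to each blinded subject for proprioceptive investigations". Neither section extends masking to anyone else, and Step 3 (treadmill gait) describes none.

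**Who handles the waveform.** In Step 2 the team writes of its configuration mapping that "we will wirelessly activate the implanted spinal paddle and compare muscle activation using LFTS and HFBS patterns". In Step 1 the third study procedure is "activation of both low-frequency tonic stimulation (LFTS) and high-frequency burst stimulation (HFBS) patterns from the inserted paddle while recording EMG signals", and the list of research procedures puts the low- versus high-frequency comparison on each contact there. Step 3 again compares the two patterns contact by contact.

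**How the EMG becomes a result.** Step 1 gives no criterion for an EMG threshold response. Step 3 allows a lead-in of about 10 seconds and then 30 seconds of recording, expected to yield ten or more successive cycles depending on cadence. The analysis is applied to consecutive cycles, and the team will use a cited method to "define modules through non-negative matrix factorization". No rule for the number of modules appears in the text.

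**Direction.** Section 1.0 expects HFBS to lower thresholds relative to LFTS (Aim 1) and to raise EMG module complexity relative to LFTS or no stimulation (Aim 3).

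**Size and model.** Section 5.0 plans 5 subjects and a two-way repeated measures ANOVA with Tukey comparisons.

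**The concern.** Masking matters most where a person turns a trace into a number. In this plan it is described only for TTDPM, where the subject's own switch stops the movement and the Biodex records the displacement. It is not described for the two EMG-based comparisons, where a reader or analyst may have to decide something. Subject masking would not help in Aim 1 in any case, because the subject is under general anaesthesia.

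At stake is the HFBS versus LFTS contrast in Aims 1 and 3. With five subjects, a small but consistent lean in reading could produce a difference or hide one. A later reader of the results could not tell such a lean from a physiological effect.

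**Working it through.** The plan states no figure on this point, so there is none to reproduce. The check is mainly documentary.

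**1. Which comparisons are exposed**

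| Measurement | What sets the value | Masking described | Open to unmasked reading of the waveform? |
|---|---|---|---|
| Step 1, MEP and SSEP thresholds (second procedure) | Evoked-potential protocols | None | No: recorded before LFTS or HFBS is switched on |
| Step 1, EMG under LFTS and HFBS (third procedure) | A reading of EMG, criterion not given | None (subject anaesthetised) | Yes |
| Step 2, TTDPM | Subject's switch and Biodex record | Subject | Not by staff reading |
| Step 3, gait EMG modules | Filtering, consecutive cycles, factorisation | None | Yes, as far as cycle window and module number are not fixed |

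**2. Does the data coding fill the gap?** Section 10.0 keeps coded and identifiable folders apart and holds a linking database between participant ID and personal identifiers. That protects identity. It is not described as hiding the stimulation condition.

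**3. Is there room in the cycle window?** Strides in 30 seconds = (steps per minute ÷ 2) × 0.5. The documents give no cadence, so these are assumed values:
- 40 steps/min: 20 × 0.5 = 10 strides
- 80 steps/min: 40 × 0.5 = 20 strides
- 100 steps/min: 50 × 0.5 = 25 strides

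At the higher cadences a run of ten could be placed in several positions. The plan says neither that all recorded cycles are used nor which run is used. If all are used, this choice disappears.

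**4. Why a small lean matters at n = 5.** This is a sensitivity range under assumption, not an estimate. Let *b* be a systematic reading bias towards HFBS, in standard deviations of the within-subject difference, with no true effect. For a two-sided 5% paired t-test with 4 degrees of freedom (critical value 2.776), the rejection rate is P(|T| > 2.776), where T is non-central t with non-centrality *b*√5.

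| Assumed *b* | *b*√5 | False-positive rate |
|---|---|---|
| 0 | 0 | 5.0% |
| 0.25 | 0.56 | 7.2% |
| 0.5 | 1.12 | 14.1% |
| 0.75 | 1.68 | 25.4% |
| 1.0 | 2.24 | 40.1% |

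The paired test is a simple stand-in for the planned ANOVA with Tukey comparisons. Nothing in the documents says which row applies, or that *b* differs from 0.

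**The case against.** The strongest reply is that the document is silent on staff masking, which is not the same as saying that staff are unmasked. **This stands in part.** Those who set the stimulation necessarily know it. That an offline analyst also knows it is an inference from the absence of any masking step. A reader might go further and suppose that the files carry waveform labels; the documents do not say so.

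Second, factorisation is algorithmic, and the cited method may fix the number of modules by a numerical criterion. **This stands.** The supportable statement is that the rule is not given here, not that the choice is subjective. Likewise, requiring consecutive cycles rules out picking single ones, though it does not fix the window.

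Third, a reader might list further exposed steps:
- *Evoked-potential thresholds.* The plan says "MEP and SSEP protocols will be performed to determine motor and sensory thresholds, respectively", but this comes before either waveform is activated, so there is no LFTS or HFBS label to influence the reading.
- *Manual artefact rejection.* The plan describes bandpass filtering and no manual step.
- *TTDPM.* The value does not come from a staff reading.

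Fourth, a reader might build an example in which judgement adds a module under HFBS in most of the five subjects, and call the resulting small p-value the effect of judgement. That result follows only from the assumed pattern, which nothing in the plan supports.

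Last, LFTS is below 100 Hz (Section 1.0) and the HFBS in the cited modelling is at 600 Hz (Section 2.0), so artefact in raw EMG could disclose the condition. **This stands** as a limit on the remedy. Partial masking is still better than none.

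**Conclusion.** The point holds in a narrow form. Masking is described for the subject during TTDPM only. None is described for the reading of LFTS and HFBS EMG responses in Aim 1 or the processing of gait EMG in Aim 3, and for gait even subject masking is not described. The document also gives no EMG threshold criterion, no fixed cycle window and no module-number rule, so a team with a directional hypothesis has room for judgement.

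The size of any bias cannot be estimated from the documents. The rates above show only how sensitive five subjects would be to an assumed lean. The conclusion rests on reading the absence of a masking step as absence from the plan, and it would weaken if the cited method or a separate laboratory procedure already fixes these choices. This is a low-priority but worthwhile improvement for a proof-of-concept study; it does not show that the results will be wrong.

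**What to change.** In Section 9.0, Step 1 (the LFTS and HFBS EMG recording) and Step 3 (the EMG module analysis), add:

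- After acquisition, a team member who does not do the reading replaces the stimulation-condition labels (LFTS, HFBS, none) with random codes.
- The EMG threshold criterion, the cycle window (for example, all complete cycles in the 30 seconds, or a fixed run) and the module-number rule are stated in advance. If the cited method already contains the module rule, one line stating it is enough.
- Offline EMG threshold reading, cycle window and module number are completed on the coded files and locked before the codes are opened.

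**Cost.** A few sentences, a relabelling step and some time from one team member who stays out of the reading. No added subjects, visits or procedures, and no change to clinical care.

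**Limits.** Stimulation artefact may partly reveal the waveform, which is why the pre-stated rules are needed as well as the codes. Choices made live, during acquisition or configuration mapping, cannot be masked this way. Nor does this supply subject masking during gait; the plan should say whether that is intended. Step 2 needs no change for this purpose.

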## **10.0 Data Management**

Once a potential participant is asked if they would like to learn more about the study, they will be assigned a participant ID. Participant IDs will be assigned consecutively. We will maintain a database that accurately reflects all potential subjects that were approached about the study and the results of eligibility evaluation. For eligible subjects, the specific types of data that will be collected include: 1) analog local field potentials from the SCS, MEP, SSEP and EMG electrodes, 2) digital and analog output signals from the IOMAX intraoperative neuromonitoring device, 3) digital, time-stamped, physical displacement data captured from the Biodex machine, 3) digital, time-stamped, positioning data produced by the PhaseSpace software, 5) videography data, and 6) any available imaging data (dicom files). Raw data will remain on our lab-owned data acquisition machines with encrypted hard drives and stored behind a locked door when not directly supervised. Data will be copied from all lab-owned data acquisition machines and/or hospital-owned data servers to a password protected network server accessible from our lab under the IRB protocol number and participant ID. This will constitute the master copy of all data for the lab and will consist of separately stored coded and identifiable folders. The purpose of keeping a copy of the raw data is in case the server is interrupted, and it is necessary to reconstruct the data. Portions of data will be copied to end-user devices (e.g., desktop, laptop, etc) for data analysis, however only the portion needed for analysis will be copied. Any end-user device such as a laptop that physically leaves the lab will be encrypted with MUSC-approved software (BitLocker, Microsoft Corp., Redmond, WA) which uses the AES encryption algorithm in cipher block chaining or XTS mode with a 256-bit key. Desktop machines used for analysis that do not leave the lab and are stored in a locked laboratory will not be encrypted. All data on data acquisition and end-user devices will be deleted at the conclusion of the study. No PHI will be stored on any data acquisition machine or end-user device. A linking database associating the participant ID and subject identifiers will be maintained on MUSC Box, separately from the research data. Subject identifiers to be collected include first and last name, gender, date of birth, social security number, medical record number, mailing address and telephone numbers. Telephone and medical record numbers are required for an approximate 7-day phone call made to subjects following SCS implantation. Additionally, we will collect information pertaining to disease severity for each subject, including Visual Analog Scale (VAS) scores, a common pain scale, and any other available rating scale scores. These measures will assist in correlating our physiological data with severity of disease for each subject. Videography data will be stored in the identifiable folder on the password protected network server. The purpose of this data is to correlate movement dynamics with physiology data. Finally, we will save imaging data on a password protected network server in order to analyze and correlate with our physiological data. Only IRB-approved personnel will have access to the linking database. Consent forms will be stored in a locked cabinet in a locked laboratory in the Clinical Sciences Building at MUSC.

## **11.0 Provisions to Monitor the Data to Ensure the Safety of Subjects**

Date: 8/1/19

Version: 01

## **Data and Safety Monitoring Plan**

The proposed research involves use of a neural stimulation device and warrants oversight by a Data Safety Monitoring Board (DSMB). The primary purpose of the DSMB is to ensure the safety of participants and the validity and integrity of data collected during the study. The overall framework involves biannual review of the enrollment, safety and adverse event data, and quality control data by the DSMB throughout the period of the proposed research.

### **DSMB composition**

The DSMB will be appointed by the PI and will be composed of individuals who are not on the study team and have the following qualifications: (1) a clinical electrophysiologist with expertise in electrical neuromodulation and intraoperative monitoring, (2) a board-certified neuropsychologist who specializes in treatment of pain syndromes, and (3) a biostatistician with expertise in design and analysis of clinical trials. These three individuals bring substantial expertise adequate to monitor data and safety for the proposed research.

### **DSMB responsibilities**

The responsibilities of the DSMB are as follows. Prior to any enrollment, the DSMB will review the study design, protocol, recruitment/enrollment plan, statistical analysis plan, and data and safety monitoring plan. Once enrollment begins, the DSMB will convene every 6 months to review the enrollment data, the safety and adverse event data and quality control data (see below for detailed data description). The DSMB will review the aggregated summary data as well as the individual participants' data (de-identified). The DSMB may provide recommendations for any safety concerns. The DSMB may recommend stopping the study early if the protocol has significant safety concerns. The DSMB will review the results and document their reviews in writing. In summary, the stopping rules are if the study has unanticipated safety concerns. The DSMB will also be able to make recommendations for appropriate action to maintain a reasonable safety profile for the study. The PI will provide a report for the IRB to review that summarizes oversight activities, DSMB recommendations and any concerns regarding participant safety.

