#### **5.0 Number of Subjects**

We propose to study 5 individuals with CLBLP. A prior study conducted by Formento et al, 2018 using SCS and proprioceptive testing published a standard error and 95% confidence interval using successful and unsuccessful SCS trial attempts ( $p < 0.05$  among LFTS parameters and no stimulation, with a minimum of 10 trials per stimulation setting). Based on this, we expect that our small population will exhibit similar variance. The subject sample size is in direct comparison to sample sizes of previous proof of concept studies regarding SCS for spinal cord physiology biomarker sampling. The research team plans to use a two-way repeated measures ANOVA model in order to investigate the varying differences in stimulation type and kinematic parameters. A Post hoc comparison will be made using a Tukey adjustment.

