#### **6.0 Setting**

The data pertaining to Aim 1 for this study will be recorded in the operating room at MUSC Main Hospital. Data collected during Aims 2 and 3 will be recorded in the Locomotor Rehabilitation Laboratory and the Locomotor Energetics and Assessment Laboratory respectively, which are both located in the College of Health Professions Building C at MUSC. Coded and identifiable data will be stored electronically on a secure server in separate folders. Signed consent forms will be located in a locked cabinet in a locked laboratory in the Clinical Sciences Building at MUSC. In all, we expect total duration of the study to be approximately 30 days for each subject.

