### **Safety reporting to the DSMB**

Subjects may report safety issues with the study directly to the PI, any member of the PI's clinical and/or research teams, the MUSC Family Care Liaison, the IRB and/or ORI Director. In the absence of any such reports, the PI will systematically attempt to uncover any safety issues experienced by a subject during the approximate one week follow-up phone call. Any of the following will be reported to the DSMB if noted by the subject during the approximate one week follow-up phone call following SCS surgery (Aim 1): severe lower back or leg pain unresponsive to pain medication, repeated falls/imbalance, excessive bleeding from wounds, lower back irritation or bleeding around the site of paddle or IPG implant and/or return to the hospital. Any of the following will be reported to the DSMB if noted during the approximate 30-day return appointment (Aims 2 and 3): return to hospital, evaluation by another provider for findings related to spinal cord stimulation surgery, imaging, lab values and/or other reports indicating complications from spinal cord stimulation surgery. All the above-mentioned issues are outside of what would be reasonably expected for a normal postoperative course following spinal cord stimulation surgery. In accordance with HRPP Section 4.7, all the above-mentioned issues constitute adverse events and will be submitted to the DSMB for review (at 6 month intervals) in addition to being recorded in an adverse event log. In addition to serious adverse events, events that are unexpected, related or possibly related to a subject's participation in the research and suggests that the research places subjects or others at greater risk of harm than was previously known or recognized constitute Unanticipated Problems Involving Risks to Subjects or Others (UPIRSOs) and must be reported directly to the IRB (in addition to the DSMB). Finally, all deaths will be reported to the IRB within 24 hours of learning of the death, unless the death is expected (e.g., due to disease progression).

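### With five subjects in the study for about 30 days each, all five can finish before the DSMB's first six-monthly review of accrued safety data

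*Combined protocol and SAP*

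**What the plan says.** Section 5.0 sets the size: "We propose to study 5 individuals with CLBLP". Section 6.0 sets the time per subject: "we expect total duration of the study to be approximately 30 days for each subject". Section 9.0, Step 2, shows what fills that time. The proprioception testing comes "Following an approximately 30-day recovery period from surgical placement of the paddle and IPG", and the walking tests follow as Step 3.

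Section 11.0 sets the oversight. Under Data and Safety Monitoring Plan, "The overall framework involves biannual review of the enrollment, safety and adverse event data". Under DSMB responsibilities, from the start of enrolment "the DSMB will convene every 6 months to review the enrollment data", along with the safety and adverse event data. The board may recommend stopping the study early over significant safety concerns; no threshold is given. Under Safety reporting to the DSMB, a list of events is defined for the one-week phone call and the 30-day visit, including repeated falls, bleeding around the implant and going back to hospital. The text calls these adverse events outside the expected postoperative course, and they "will be submitted to the DSMB for review (at 6 month intervals").

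Other routes exist. UPIRSOs go directly to the IRB and also to the DSMB. Deaths, unless expected, go to the IRB within 24 hours. There is also a review before any subject is enrolled: "Prior to any enrollment, the DSMB will review the study design, protocol, recruitment/enrollment plan", together with the analysis plan and the monitoring plan itself.

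**The concern.** The protocol says that this research warrants a DSMB and gives the board a say in whether the study continues. That say has effect only if the board sees subject data while subjects remain to be protected. The only scheduled reviews of accrued data follow the calendar, and the interval is about six times one subject's stay. No review is triggered by the number of subjects treated, by a subject completing, or by an event.

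The events on the slow route are relevant. Section 13.0 attributes to the research a slightly raised infection risk (longer surgery, terminals connected outside the surgical field, extra personnel) and a risk of falls during the walking tests. A pattern of such events in the first subjects is what an independent board would want to see before the later ones. On the present schedule it might see them only after the last subject has left.

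**Working it through.** There is no plan figure to reproduce; the check is a timeline.

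**Inputs from the protocol**
- Subjects: N = 5 (section 5.0).
- Time in study from surgery: D = 30 days (sections 6.0 and 9.0).
- DSMB interval: 6 months, R = 365.25 / 2 = 182.6 days, counted from the start of enrolment (section 11.0).

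**Assumptions, because the protocol is silent**
- The first data meeting falls a full interval after enrolment begins.
- Surgeries are evenly spaced, g days apart. No accrual rate or accrual period is given, so g is varied.
- The lag L from first consent to first surgery is 0, 14, 30 or 60 days. Consent may be given at the preoperative clinic visit or on the morning of surgery (section 8.0), so L = 0 is possible but not assured.

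**No overlap between subjects, L = 0.** 5 × 30 = 150 days, which is 182.6 − 150 = about 33 days before the first data review. Fast or overlapping accrual is not needed.

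**Largest gap at which all five finish first.** The last subject finishes at L + 4g + 30. Setting this no later than 182.6 gives g ≤ (152.6 − L) / 4.

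| Lag L (days) | Largest gap g (days) |
|---|---|
| 0 | 152.6 / 4 = 38.2 |
| 14 | 138.6 / 4 = 34.7 |
| 30 | 122.6 / 4 = 30.7 |
| 60 | 92.6 / 4 = 23.2 |

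**Position at the first data review, L = 0.** Subject i (i = 0 to 4) has surgery on day g × i and finishes on day g × i + 30.

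| Gap g (days) | Last subject finishes (day) | Finished by day 182.6 | Past surgery by day 182.6 |
|---|---|---|---|
| 7 | 58 | 5 of 5 | 5 of 5 |
| 14 | 86 | 5 of 5 | 5 of 5 |
| 30 | 150 | 5 of 5 | 5 of 5 |
| 38 | 182 | 5 of 5 | 5 of 5 |
| 45 | 210 | 4 of 5 | 5 of 5 |
| 60 | 270 | 3 of 5 | 4 of 5 |
| 90 | 390 | 2 of 5 | 3 of 5 |

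At a 45-day gap one subject is unfinished, but all five have already had the intraoperative research procedures.

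**The case against.** **Accrual could be slow.** A reader might infer that the 6-month interval is longer than the study is likely to last. The documents do not support that. They give no accrual rate, accrual period or surgical volume, and section 11.0 describes recurring reviews over the research period, which suggests that more than one was expected. Only the statement that all five can finish first is supportable. At gaps of 2 to 3 months, 2 or 3 subjects would still be unfinished at the first review and the board could act for them. The 38-day limit also shrinks if the clock starts at consent.

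**Other safeguards exist.** A reader might infer that the DSMB hears nothing between meetings. That is too strong. The UPIRSO route includes the DSMB and carries no 6-month limit. The opening of that sentence could also be read as covering serious adverse events, though it is ambiguous. The board reviews the monitoring plan before enrolment and could question the interval then. Subjects are called at about one week and checked at about 30 days, they may report directly to the IRB, and section 12.0 lets the team end data collection for a subject.

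These points narrow the concern without removing it. The UPIRSO route has no deadline and no ad hoc meeting, and it applies only to events already judged to qualify. A listed event not so classified waits for the 6-month submission. The death route leads to the IRB. The team's power in section 12.0 is over one subject and is not independent review of the study. The pre-enrolment review contains no subject data.

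**The research increment is small.** This stands. The implant is placed for clinical reasons whether or not the patient takes part. The research adds about 15 minutes to surgery plus harnessed walking and testing that the subject can halt. Many listed events could follow the clinical surgery itself, and stopping the research would not remove that risk. What is at stake is the protection of subjects against the added research risk only.

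**Conclusion.** The concern holds as a gap in what the schedule guarantees. The passages in section 11.0 agree with one another on the interval, so this is a design choice and not an internal contradiction. On the protocol's own figures, all five subjects can finish before the DSMB's first review of accrued data. This happens when surgeries are up to about 38 days apart, or up to about 23 to 35 days apart if the clock starts at consent and surgery follows 60 to 14 days later. At gaps of 2 to 3 months (clock from first surgery), 2 to 3 of the 5 finish first. In the faster cases the board's power to recommend stopping would never operate while a subject is exposed to research risk.

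The result depends on accrual, which is not stated, on even spacing, and on the first data meeting falling a full six months after enrolment begins. It does not show that the study will be over by then, or that no event can reach the DSMB sooner. The change is worth making because it closes the gap at almost no cost.

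**What to change.** Amend section 11.0 as follows.

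1. In Safety reporting to the DSMB, replace the 6-month submission of listed events with circulation to the DSMB when each event is logged, within a number of days that the sponsor states. State a time limit for sending UPIRSOs to the DSMB as well, and say plainly whether serious adverse events follow the same route.
2. In DSMB responsibilities, allow an ad hoc review when such a report calls for one.
3. Add a short written review by email, triggered by subject count, for example after the first and third subjects complete Step 3.
4. Keep the 6-month meeting as a backstop.

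The count-triggered reviews should carry no mandatory pause in enrolment and no effect on clinically scheduled surgery, and the amendment should say so. Aim 1 data can be collected only at that surgery, and Aims 2 and 3 use the same subjects. Holding research procedures until a review is complete could lose an eligible patient from all three aims, a real cost in a study of five.

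The cost is amendment wording, two brief email reviews and some extra administration for the DSMB and the study team.
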